Our *long-term goal* is to develop and implement dietary intervention(s) that reduce risk of T2D. The *overall goal of this randomized controlled trial is to study the effect of a behavioral intervention promoting a low-carbohydrate/high-unsaturated fat and high-protein dietary pattern (initial target <40 g digestible carbohydrates, final target <60 g digestible carbohydrates) compared with a usual diet on metabolic risk factors among individuals with prediabetes or early-stage untreated diabetes (HbA1c 6.0–6.9%).* Specifically, we will test the following hypotheses:

Primary hypothesis: Compared with usual diet, over a 6-month period, a healthy low-carbohydrate/high unsaturated fat and high-protein dietary pattern will lead to a larger decrease of HbA1c, by at least 0.15%.

Secondary hypothesis: Over a 6-month period, a healthy low-carbohydrate/high-unsaturated fat and high-protein dietary pattern will lead to larger improvements in the following major secondary outcomes: fasting glucose, systolic blood pressure (BP), total-to-HDL-cholesterol ratio, and body weight.

Exploratory outcomes: We will also study the effect of the intervention on the 6-month change in: insulin and homeostasis model assessment of insulin resistance (HOMA-IR); diastolic BP; waist circumference; and estimated CVD risk.

To achieve these study aims, we will recruit 150 adults with prediabetes or untreated diabetes (HbA1c 6.0–6.9%) in the Greater New Orleans, LA area. Using a stratified, blocked randomization scheme, participants will be assigned to either a behavioral modification intervention aimed at promoting a healthy low-carbohydrate dietary pattern or to usual diet. The intervention group will have an intensive phase for 3 months, followed by a maintenance phase in months 4 through 6. The primary outcome will be difference between the active intervention and control groups in the change in HbA1c from baseline to 6 months of follow-up. We expect 80% power to detect a difference of at least 0.15% in change of HbA1c. Changes in other metabolic risk factors will be studied concurrently. Metabolic risk factors will be assessed at baseline, 3 months, and 6 months of follow-up.

There is much interest regarding dietary approaches to prevent T2D and its complications. The results from this study will help to determine whether, compared with usual diet, a behavioral intervention aimed at promoting a healthy low-carbohydrate dietary pattern improves metabolic risk factors.

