7.A.3. Referrals and Local Partnerships: In addition to local physician referrals, we will explore holding outreach community events in the New Orleans area. Local community partners may post information about the study on their social media platforms. We may also identify potentially interested volunteers from a Tulane volunteer recruitment registry. We will also consider recruiting potentially eligible individuals who were screened or participated in other clinical studies in our clinic and have expressed interest in being contacted about future research projects. Potential participants referred by their physician or community partners will have a pre-screening telephone interview to confirm potential eligibility. Those who are still interested and potentially eligible for the study will be scheduled for a screening visit.

7.B. Randomization

Once eligibility has been confirmed, the study coordinator will ensure that all key variables have been entered into the trial-specific database. Additionally, the study coordinator will ensure any outliers have been recognized and reconciled, and will ensure receipt of informed consent prior to enrolling the volunteer in the study as a trial participant. Eligible participants will be randomly assigned to the behavioral intervention or the usual diet group in a 1:1 allocation ratio. Randomization will be stratified by sex, using a random block group size (4, 6) to maintain balance among groups over time. A statistician from the Methodology/Biostatistics Unit within the COBRE Clinical Research Core, who is not directly involved in the study and is not located at the clinic, will conduct the randomization. After ascertaining eligibility, clinical personnel will telephone the Methodology/Biostatistics Unit to obtain a randomization assignment. All randomization assignments will be created by a computer program and only accessible to the Staff at the Methodology/Biostatistics Unit. Once randomization assignment has been made, trial participants will be considered to be officially randomized into the study and every effort will be made to obtain complete follow-up information.

7.C. Masking

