10.B.3. Assessment and management of adverse effects: At RZ, 3-month visit, and 6-month TV, we will administer *symptom questionnaires*, which will consist of a checklist to identify participant complaints. Prior studies of low-carbohydrate dietary interventions suggest that participants may experience a range of adverse effects, including constipation, halitosis, fatigue, headache, thirst, polyuria, and nausea. Severe adverse events will be promptly reported to the DSMB. Management of adverse effects will be based on the protection and safety of the participant. If severe adverse effects are reported by a participant, carbohydrate intake will be examined and altered in order to mitigate the adverse effect. In any extreme cases, participants will be instructed to stop the intervention. As this is a behavioral intervention, adverse effects should be rare.

10.B.4. BP and anthropometric measures: BP will be measured 3 times at the screening visit and at each follow-up visit. To minimize random error, averages of the measurements at the screening and randomization visits will be taken. BP will be measured by a standard automated blood pressure measurement device (OMRON HEM-907 XL Professional Digital Blood Pressure Monitor) and performed by experienced staff, trained and certified in BP measurement. Prior to BP measurements, participants will be asked to rest quietly in a seated position with their feet supported for at least 5 minutes; staff members will use an appropriate cuff size over a bare arm. Trained and certified staff will measure weight using a calibrated balance beam scale at the screening visits, and follow-up visits. Weight and height will be measured at the RZ, and weight will also be measured at the subsequent visits.

10.B.5. Blood samples: For SV, participants will not need to fast. For RZ, 3-month visit, and 6-month TV, participants will be instructed to fast for 12 hours prior to blood sample collection. At SV, blood samples will be collected to measure HbA1c, hemoglobin, and serum creatinine. At RZ, fasting blood samples will be collected and stored as serum/plasma, whole blood aliquots and buffy coats at -80°C for future analyses, including measurement of glucose, insulin and lipids, and potential future metabolomics or genetic analyses. At 3-month visit and 6-month TV,

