we will collect fasting blood samples to measure HbA1c and will also store additional serum/plasma, whole blood aliquots and buffy coats at -80°C for future analyses, including measurement of glucose, insulin and lipids, and potential future metabolomics or genetic analyses. Details of the blood sample collection are shown in **Table 4**. In the event that a participant moves, we may request that they collect a fasting blood sample at a local LabCorp and we will measure HbA1c, glucose, insulin, and lipids at the 3 and 6-month visits. HOMA-IR will be calculated from fasting glucose and insulin.

HbA1c will be measured at LabCorp (Roche Tina Quant; fresh samples) from whole blood collected at screening, 3-month, and 6-month visits. Following trial completion, to improve precision of HbA1c estimates, HbA1c will also be measured at the Diabetes Diagnostic Laboratory (ion-exchange method; Tosoh G8 HPLC Analyzer; frozen samples) from whole blood collected at randomization, 3-month, and 6-month visits. Samples with Hb variants (C, D, E, S) that are measured at the Diabetes Diagnostic Laboratory will be reflexed for measurement by boronate affinity HPLC (Trinity Premier Hb9210).¹¹³

Table 4. Study visit schedule for specimen collection

	SV	RZ	3 month	6 month TV
HbA1c	X		X	X
Serum creatinine	X			
Hemoglobin	X			
Storage of aliquots and buffy coats (for measurement of glucose, insulin, lipids, other potential future measurements)		X	X	X
Urine sample for pregnancy	X			
Urine sample for ketones and other markers		X	X	X
Stool sample		X	X	X
CGM				X

10.B.6. Urine collection: Study staff will collect spot urine specimens at RZ, interim visit, and the final visit to measure ketones.

10.B.7. Stool Specimen Collection: Stool samples will be collected from all eligible and willing trial participants during the RZ, 3-month, and 6-month TV, following the protocol set forth by the Human Microbiome Project.^{114,115} Participants will be given a stool collection kit, which includes the specimen collection container, a shipper for home collection, and a form to record the timing and pertinent information related to specimen collection. Participants will be instructed to return the kit to the clinic within two days of collection (in-person or via shipping), at which time stool samples are stored at -80°C until analyses. Kits and instructions for collection will be reviewed by study staff with the participant at the required visits.

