Trial personnel will all be required to participate in a training session before the start of any trial procedures or measurements. Training will include particular attention to core trial elements, such as recruitment, retention, intervention, completeness and quality of data acquisition (e.g., blinding procedures for the data collectors), and data entry. Separately, intervention staff will meet and receive detailed instruction on trial approaches to group and individual behavior change counseling and procedures that ensure data collectors are blinded to treatment assignment. Throughout the trial, periodic re-training/certification sessions will be conducted to ensure all trial-related procedures are being applied in a standard manner. Investigators will also monitor all aspects of study performance to ensure study goal achievement, timeliness and completeness of study visits, completeness and quality of data collection, intervention adherence, and adequacy of the procedures separating data collection from intervention. Study staff and investigators will pay particularly careful attention to the quality of all laboratory measurements, particularly key exposure, outcome, and intervention monitoring variables.

12. Sample Size and Statistical Power

The primary outcome will be the difference in the change of HbA1c between the intervention and usual diet groups from baseline to 6 months of follow-up. Preliminary data from ADEPT suggests that the SD of the 6-month change in HbA1c is 0.28%, with preliminary 6-month follow-up >90%. Based on an estimated standard deviation of change in HbA1c of 0.35% and 95% follow-up, we would need 142 participants to have 80% power to detect a difference in the change in HbA1c from baseline to 6 months of 0.17% between the intervention and usual diet groups. Assuming 95% follow-up, we would need 150 total participants.

In a follow-up analysis of the DPP, a 0.15% decrement in HbA1c at 6 months was associated with a 16% lower risk of incident T2D, adjusting for treatment arm, age, sex, race/ethnicity, household income, and baseline HbA1c.¹¹⁶ In a pooled analysis from the Atherosclerosis Risk in Communities and Framingham Heart Studies, a 0.15% higher HbA1c was associated with an 16% higher risk of T2D over 20 years, a 30% higher risk over 8 years, and a 13% higher risk after 8 years, after adjusting for age, sex, fasting glucose, triglycerides,

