HDL, family history of T2D, SBP, and BMI.¹¹⁷ Additionally, in EPIC-Norfolk, a difference of HbA1c of 0.15% was associated with approximately a 5% higher risk of CHD among those free of CHD, stroke, diabetes, and with HbA1c <7.0%.¹¹⁸

In the DPP study, HbA1c was 0.15% lower among those in the lifestyle intervention arm than in the control arm at 6-months follow-up; HbA1c at study commencement was 5.9% and levels increased in the control arm and decreased in the behavioral intervention arm.²² In a small behavioral intervention study (n=34) of a very low-carbohydrate ketogenic diet compared with a moderate carbohydrate, calorie-restricted, low-fat diet among individuals with type 2 diabetes or prediabetes (HbA1c >6.0%) and elevated body weight (BMI >25), mean HbA1c

decreased from 6.6% to 6.1% in the very low-carbohydrate group and from 6.9% to 6.7% in the moderate carbohydrate group over a 12-month period; additionally, the very low-carbohydrate group had greater reductions in glucose-lowering medications.³⁷

Detectable differences are listed for HbA1c and secondary outcomes in **Table 5**, based on data from prior studies.^{30,53,56,119} These were calculated for unpaired t-tests, power of 80%, two-sided alpha of 0.05, and assuming 95% follow-up of 150 participants, which would yield an estimated 142 participants.

Table 5. Minimum detectable differences

Change from baseline to 6 months in	SD	Detectable Difference
HbA1c, %	0.35	0.17
Fasting glucose, mg/dL	12.5	5.9
Fasting insulin, mU/mL	7.0	3.3
HOMA-IR	2.0	0.95
SBP (mmHg)	4.2	2.0
DBP (mmHg)	3.0	1.4
Total/HDL ratio	1.2	0.57
Body weight (kg)	6.6	3.1
Waist circumference (cm)	8.0	3.8
Estimated CVD risk (%) [*]	6.7	3.4

*10-y CVD risk, among estimated 85% or 126 participants free of CVD

13. Data Management and Analysis

13.A. Data management

Personnel will double-enter all study data. Prior to entering data, the study coordinator will conduct quality control on all study forms, study measures, and laboratory data. Data will be cleaned and logically checked.

13.B. Data analysis plan

The data will be analyzed using *intention to treat*; this involves comparing the primary and secondary outcomes between participants based on randomization assignment.

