13.B.1. Exploratory data analysis: We will express group data for variables with a normal distribution as mean \pm standard deviation and for variables not normally distributed as median and interquartile ranges (or will log-transform the variables to obtain a normal distribution). We will compare means and percentages of baseline variables across the intervention and usual diet group to assess similarity of these groups at randomization.

13.B.2. Primary, secondary, and exploratory outcomes: We will test the primary study hypothesis that there is a greater reduction in HbA1c from baseline to 6 months in the intervention group than in the usual diet group. To do this, we will use linear regression with change in HbA1c from baseline to 6 months as the dependent variable

We will use Bland-Altman plots to explore whether there is a systematic difference in HbA1c measured by LabCorp compared with DDL. If there is not a systematic difference in HbA1c measured at these two laboratories, to improve precision in the estimate of the primary outcome (difference in change in HbA1c between the intervention and control groups), we will use the weighted average of change in HbA1c measures from the two labs as the outcome (weights defined as the ratio of the variance for each lab over the sum of the variance) (50). If we observe a systematic difference between HbA1c measured at LabCorp and DDL, we will use HbA1c measured at DDL.

We will use a similar approach to test the difference in the change between baseline and 6-month values of secondary outcomes (Specific Aim 2) and exploratory outcomes. In exploratory analyses, we will also test the difference in the change between baseline and 3-month values of outcomes (HbA1c, fasting glucose, systolic blood pressure, total-to-HDL cholesterol, body weight, insulin, HOMA-IR, diastolic blood pressure, waist circumference, and estimated CVD risk). We will also explore the use of mixed effects models to assess overall net change in HbA1c (by treating time as a linear variable) and other outcomes over the full study period. For each outcome, we will test modeling assumptions and will consider transformation of outcomes, if needed, to meet modeling assumptions. We will also perform sensitivity analyses using Markov-chain Monte Carlo techniques to impute missing values of the outcomes, using covariates for this imputation and will compare results from this analysis with our primary findings.

15. Anticipated Challenges

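### The primary HbA1c model, as supplied, names no covariates; adding baseline HbA1c and sex would be a cheap, modest improvement and does not correct an error

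*Combined protocol and SAP*

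**What the plan says.** Section 13.B.2 states the primary model in one sentence: "we will use linear regression with change in HbA1c from baseline to 6 months as the dependent variable". It has no closing full stop and does not name the arm term. No other section lists a term for this model. Section 13.B adds only that analysis is by intention to treat. Secondary and exploratory outcomes are to follow a similar approach. Covariates appear in the analysis plan only for the sensitivity analysis that imputes missing outcomes, and they are not listed there.

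On design, section 7.B says: "Randomization will be stratified by sex, using a random block group size (4, 6) to maintain balance among groups over time". Section 12 describes the detectable differences in Table 5 this way: "These were calculated for unpaired t-tests, power of 80%, two-sided alpha of 0.05", with 142 evaluable out of 150.

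Section 10.B.5 gives HbA1c two baselines. For the first laboratory, "HbA1c will be measured at LabCorp (Roche Tina Quant; fresh samples) from whole blood collected at screening, 3-month, and 6-month visits". The Diabetes Diagnostic Laboratory measures frozen samples "from whole blood collected at randomization, 3-month, and 6-month visits". Under 13.B.2 the outcome is either a weighted average of the change at the two laboratories or, if they differ systematically, the second laboratory alone.

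**The concern.** In a change-score analysis the baseline value is often related to the change, and a stratification factor may be related to the outcome. Leaving both out gives up whatever variance they explain, although the data are in hand. The wording also leaves the primary model short of a full statement, and the other outcomes inherit it. Terms fixed now cannot become a choice made after the data are seen. The two laboratory baselines add a detail that adjustment would have to settle: which baseline goes with which version of the outcome.

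At stake are some precision and a complete specification. Bias is not at stake.

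**Working it through.** **Inputs from the documents.** SD of change 0.35, difference 0.17, 142 evaluable (71 per arm), two-sided alpha 0.05 (section 12). Section 1 hypothesises that the diet "will lead to a larger decrease of HbA1c, by at least 0.15" (percent HbA1c). Section 12 also reports: "Preliminary data from ADEPT suggests that the SD of the 6-month change in HbA1c is 0.28%, with preliminary 6-month follow-up >90". Eligibility is HbA1c 6.0-6.9% (section 6.A).

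**Assumptions, not in the documents.** Slope of change on baseline -0.1 to -0.5. Baseline SD 0.20 to 0.26; the upper value is a uniform spread over the eligibility range, 0.9/√12 = 0.26.

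**1. The plan's own figure.** SE = 0.35 × √(4/142) = 0.0587. With a noncentral t on 140 df, the difference detectable with 80% power is 0.166, which rounds to the stated 0.17. Power at exactly 0.17 is 82.0%; at 0.15 it is 71.8%. With SD 0.28, power at 0.15 is 88.7%. The sizing therefore matches an unadjusted comparison.

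**2. Validity of the unadjusted model.** Simulation with sex-stratified blocks of 4 and 6 (N = 142, 8,000 runs per setting) gave bias within 0.001 and type I error of 4.7-5.4%. If sex is prognostic, omitting it makes the test slightly conservative. With half women and a sex difference of d SDs in change, R² = d²/4 and type I error = 2 × P(T₁₄₀ > 1.977/√(1 - R²)). That is 4.9% at d = 0.2 and 4.3% at d = 0.5 (d assumed).

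**3. Adjusted power.** R² = (slope × baseline SD / SD of change)². Residual SD = 0.35 × √(1 - R²). Degrees of freedom are 142 - 4 = 138. The variance is multiplied by 1.0082 for chance covariate imbalance (simulated under the planned stratified blocks, 20,000 runs) or by 1 + 2/(142 - 5) = 1.0146 if both covariates are left to chance.

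Example, slope -0.5 and baseline SD 0.26: R² = (0.5 × 0.26/0.35)² = 0.138. Residual SD = 0.325. SE = 0.325 × √(1.0082 × 4/142) = 0.0548. Noncentrality is 0.17/0.0548 = 3.10, giving 86.9% power, and 0.15/0.0548 = 2.74, giving 77.6%.

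Ranges below run over both baseline SDs and both variance factors.

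| Slope | R² | Power at 0.17 (unadjusted 82.0%) | Power at 0.15 (unadjusted 71.8%) |
|---|---|---|---|
| -0.1 | 0.003-0.006 | 81.5-81.9% | 71.3-71.6% |
| -0.2 | 0.013-0.022 | 81.9-82.5% | 71.7-72.4% |
| -0.3 | 0.029-0.050 | 82.5-83.5% | 72.4-73.6% |
| -0.4 | 0.052-0.088 | 83.4-85.0% | 73.4-75.3% |
| -0.5 | 0.082-0.138 | 84.5-86.9% | 74.8-77.6% |

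**4. Break-even and downside.** Adjustment pays once R² exceeds about 0.8-1.5%, a slope of about -0.12 to -0.21. With R² = 0, power at 0.15 falls from 71.8% to 71.1-71.4%, a loss of about 0.4 to 0.6 point before rounding.

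**5. What 80% at 0.15 would take.** At SD 0.35 it needs R² of about 0.19. From baseline alone that is a slope of about 0.35 × √0.19/0.26 = 0.59 in size at baseline SD 0.26, or 0.35 × √0.19/0.20 = 0.76 at 0.20.

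**The case against.** The strongest reply is that nothing is wrong. The sentence is visibly incomplete, and the missing words may have been lost when the PDF was read, in which case the plan may already name its terms. Taken literally, it fixes a valid unadjusted model that agrees with the sizing, and that is a legitimate choice. The slope and baseline SD are assumed throughout. At weak slopes the effect is nil or slightly negative, and power at the planned 0.17 is already 82.0%. The baseline SD of 0.26 describes the screening sample that decides eligibility. The second laboratory's baseline is a randomization sample on another assay, which eligibility does not truncate, so the range may not suit it.

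All of this stands, and it limits the point to an inexpensive improvement. It does not remove the case for naming the terms if the source page is silent.

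Two stronger readings should be resisted. A reader might infer that analysing without the stratification factor biases the estimate or inflates type I error. The checks show no bias, and error at or slightly below 5%. A reader might also infer that adjustment closes the power gap between the hypothesised 0.15 and the planned 0.17. Within the assumed ranges it does not. Nor can that be ruled out absolutely: a slope of -0.6 with baseline SD 0.26 would give 80.3-80.5%. The gap between 0.15 and 0.17 is a separate sample-size matter and lends this point no support.

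**Conclusion.** The point holds as an improvement to specification and precision, subject to the source page. The unadjusted comparison is valid and consistent with its sizing. With SD 0.35 and 142 evaluable, adding baseline HbA1c and sex changes power at the planned 0.17% by between about -0.5 (82.0% to 81.5%) and +4.9 points (82.0% to 86.9%). At 0.15% the change is between about -0.5 (71.8% to 71.3%) and +5.8 points (71.8% to 77.6%). These ranges rest wholly on the assumed slopes and baseline SDs and credit no variance to sex. The gain is modest because the narrow HbA1c entry range limits how much variance baseline can explain. The more dependable benefit is a fully stated primary model.

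**What to change.** Check the source page for the rest of the sentence in 13.B.2. If it names no terms, state the primary model as 6-month change in HbA1c regressed on arm, baseline HbA1c and sex.

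Define baseline to match the outcome: the screening sample for the first laboratory, the randomization sample for the second, and the same laboratory weights if the outcome is the weighted average.

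Use the same form, each with its own baseline, for every secondary and exploratory change outcome. For blood pressure, section 10.B.4 already describes a suitable baseline: "To minimize random error, averages of the measurements at the screening and randomization visits will be taken". Include baseline and sex in the imputation model as well, so that a difference from the primary result reflects the handling of missing data and not a different covariate set.

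The cost is SAP wording; no new data, visits or participants are needed. Statistically it is two degrees of freedom and 0.8-1.5% of variance from chance covariate imbalance.

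### The two-laboratory average that forms the primary outcome weights each laboratory in proportion to its variance, not inversely, so the noisier laboratory counts for more and precision can be lost.

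*Combined protocol and SAP*

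**What the plan says.** Section 10.B.5 describes two HbA1c series. The first: "HbA1c will be measured at LabCorp (Roche Tina Quant; fresh samples) from whole blood collected at screening, 3-month, and 6-month visits". The second comes from the Diabetes Diagnostic Laboratory (DDL), run after trial completion ("ion-exchange method; Tosoh G8 HPLC Analyzer; frozen samples) from whole blood collected at randomization, 3-month, and 6-month visits").

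Section 13.B.2 makes the primary outcome depend on a Bland-Altman comparison of the two. If no systematic difference is found, "we will use the weighted average of change in HbA1c measures from the two labs as the outcome", with "weights defined as the ratio of the variance for each lab over the sum of the variance". The reason given is "to improve precision in the estimate of the primary outcome". In the other case: "If we observe a systematic difference between HbA1c measured at LabCorp and DDL, we will use HbA1c measured at DDL".

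The weighting rule carries a parenthetical citation, number 50. Section 10.B.5 repeats the precision aim but gives no weights. Neither section says which variance is meant (assay error, or the variance of the 6-month change) or whether it is pooled over arms.

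**The concern.** Read literally, the weight for laboratory i is v_i/(v_1+v_2). The laboratory with more variance always receives more than half the weight, which is the reverse of what a precision argument calls for. Nothing else in the document mentions inverse or reciprocal weights. Item 50 in the bibliography is a report on Mediterranean diets and metabolic syndrome from a randomised diet trial, so the citation does not let a reader recover another formula.

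The rule defines the primary endpoint whenever the laboratories agree on average. Followed as written, it yields a larger standard error than a simple average whenever the variances differ, and it can do worse than discarding the noisier laboratory. If the analyst assumes that a word was dropped and inverts the weights, that departs from the stated endpoint definition, and it happens after outcome data exist. Either way there are two candidate primary estimates.

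**Working it through.** **Inputs from the document.** Allocation is 1:1 (section 7.B). Of 150 participants, 142 are expected to complete, so 71 per arm, with an unpaired t-test at two-sided 0.05 and 80% power (section 12, Table 5). The planning SD of change is 0.35% and the preliminary SD 0.28% (section 12). The primary hypothesis names a difference of 0.15% (section 1). No variance is given for either laboratory.

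**The plan's own figure.** With SD 0.35 and 71 per arm, the detectable difference is 0.35 × (1.960 + 0.842) × √(2/71) = 0.165 by the normal formula and 0.166 by the t-test. Both round to the 0.17 in Table 5. That calculation does not use the weighting rule.

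**General result.** Let V1 > V2 be the variances of the two laboratories' changes and C their covariance. With weight w on laboratory 1,

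Var(w) = w²V1 + (1−w)²V2 + 2w(1−w)C.

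Write w = ½ + d for the rule as written, with d = (V1−V2)/[2(V1+V2)]. Inverse-variance weighting is then w = ½ − d, and

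Var(½ ± d) = (V1+V2+2C)/4 ± d(V1−V2) + d²(V1+V2−2C).

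- As written minus inverse: 2d(V1−V2) = (V1−V2)²/(V1+V2). C cancels. The excess is never negative and is zero only if V1 = V2.
- As written minus equal weights: d(V1−V2) + d²(V1+V2−2C). The second term cannot be negative, because V1+V2−2C is the variance of the between-laboratory difference. The rule is therefore never better than a simple average.

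**Against the better laboratory alone.** Put r = V1/V2 and c = C/V2. The rule is worse than laboratory 2 alone when r² − r − 2 + 2c > 0, that is, when r > [1 + √(9−8c)]/2. The threshold is 2.0 at c = 0, 1.62 at c = 0.5, 1.37 at c = 0.75 and 1.17 at c = 0.9.

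**Assay error only** (independent errors, in units of the better laboratory's error variance): the rule gives (r²−r+1)/(r+1), inverse weighting r/(r+1), equal weighting (1+r)/4.

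| r | as written | equal | inverse |
|---|---|---|---|
| 1.5 | 0.70 | 0.625 | 0.60 |
| 2 | 1.00 | 0.75 | 0.667 |
| 3 | 1.75 | 1.00 | 0.75 |

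These are ratios of the error component, not of the trial's full standard error, which also contains true between-person change.

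**Illustration on the outcome scale (assumed).** Take the section's two SDs as if they belonged to the two laboratories: V1 = 0.35² = 0.1225 and V2 = 0.28² = 0.0784, so r = 1.56. Take C = 0.05, a correlation of 0.05/(0.35 × 0.28) = 0.51. The noisier laboratory's weight is 0.1225/0.2009 = 0.61.

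- As written: 0.61² × 0.1225 + 0.39² × 0.0784 + 2 × 0.61 × 0.39 × 0.05 = 0.0813 with unrounded weights; SD 0.285.
- Inverse: 0.0716; SD 0.268. The gap is 0.0441²/0.2009 = 0.0097, as the formula predicts.
- Equal: 0.0752; SD 0.274.
- Better laboratory alone: 0.0784; SD 0.280.

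Power for 0.15% (t-test, 71 per arm) is 87.6%, 91.3%, 89.9% and 88.7% respectively. The variance ratio 0.0813/0.0716 = 1.135 is equivalent to 142/1.135 ≈ 125 completers, a loss of about 17.

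**Range over the correlation**, same SDs:

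| correlation | SD (power) as written | equal | inverse | better laboratory alone |
|---|---|---|---|---|
| 0.6 | 0.292 (85.9%) | 0.282 (88.2%) | 0.275 (89.7%) | 0.280 (88.7%) |
| 0.7 | 0.300 (84.0%) | 0.291 (86.3%) | 0.284 (87.9%) | 0.280 (88.7%) |
| 0.8 | 0.308 (82.2%) | 0.299 (84.3%) | 0.292 (86.0%) | 0.280 (88.7%) |

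**A milder case.** With true-change SD 0.25 and error SDs 0.15 and 0.10 (all assumed), the SD is 0.267 as written, 0.265 inverse and 0.269 for the better laboratory alone. Averaging still helps slightly.

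**The case against.** The strongest reply is that this costs a little efficiency and threatens nothing else. The weights are common to both arms and apply only when no systematic laboratory difference is seen, so the rule does not itself bias the comparison. If a difference is seen, DDL alone is used and the weights never operate. With fresh samples at one laboratory, frozen at the other, and different assay methods, that fallback is a real possibility. In the main illustration the loss is 1.1 power points against the better laboratory (88.7 − 87.6) and 3.7 against inverse weighting (91.3 − 87.6), and power stays above 80%. The laboratory variances are assumed, and with equal variances nothing is lost. The stated aim also suggests that the word inverse was simply left out.

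All of that stands as a limit on size, but it does not rescue the rule. The aim and the formula contradict each other, and nothing in the document says which should give way.

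A second objection concerns the remedy: inverse weights built on total variances of change can also lose to the better laboratory alone. That is correct, as the rows for correlations 0.7 and 0.8 show, because the two changes share the true change. Such weights are not fully optimal. They are still never worse than the rule as written.

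**Conclusion.** The concern holds. As written, the rule for the primary outcome weights toward the noisier laboratory and works against its own stated purpose. That it is never more precise than equal or inverse-variance weighting is exact algebra and needs no assumed figures. It is less precise than the better laboratory alone once the variance ratio exceeds 2 with uncorrelated laboratories, and at lower ratios when they are positively correlated.

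The size in this trial is unknown because no laboratory variances are given. With assumed SDs of 0.35% and 0.28% and correlations from 0.51 to 0.8, power for 0.15% is 87.6% down to 82.2% as written, against 91.3% down to 86.0% with inverse-variance weights and 88.7% with the better laboratory alone. The loss is one of precision, arises only when the averaging branch is used, and leaves the sample-size calculation untouched. It should be corrected before the arms are compared, because the sentence defines the primary endpoint.

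**What to change.** In section 13.B.2, replace the weights with w_LabCorp = v_DDL/(v_LabCorp + v_DDL) and w_DDL = v_LabCorp/(v_LabCorp + v_DDL). Equal weights are an acceptable simpler choice: they need no variance estimate and are never worse than the present rule.

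State what v is, since the choice changes the weights: either the variance of the 6-month change, pooled within arms under masked arm codes, or the assay error variance. The second is the better target if the laboratories prove highly correlated, because it leaves out the true change that both share. Fix the weights before the treatment comparison is run. Replace citation 50 with a source for the weighting method.

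The cost is a sentence or two of analysis-plan wording. No new data are needed, and relative to the present rule there is no loss of precision.
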